### 3.5 Analysis Plan

#### **Hypothesis 1.1 $PTSD_{dx}$ will discriminate PTSD patients from control subjects without PTSD;**

The primary evaluations will be based on computation of  $PTSD_{dx}$  and  $PTSD_{sev}$  markers similar to the approach used in preliminary studies. This will occur in multiple phases, all of which will randomly divide and analyze the full sample of 656 veterans into 3 groups of 219, 219, and 218 subjects, and in proportion to the presenting symptom/condition status of veterans, as follows:

Condition (Group)	Total N	Subsample		
		Sample 1	Sample 2	Sample 3
PTSD only (group A)	107	36	36	35
TBI only (group B)	126	42	42	42
PTSD & TBI (group C)	87	29	29	29
Depression only (group D)	80	26	27	27
Controls (no PTSD, TBI, depression) (group E)	256	86	85	85

To test our first hypothesis and in the first phase of analysis, we will use the specific  $PTSD_{dx}$  neuromarker previously identified in our preliminary study of 76 veterans, and evaluate it separately in all 3 subsamples. Analysis of covariance (ANCOVA) will be used to compare adjusted mean  $PTSD_{dx}$  scores between the PTSD only group (Group A) vs. planned contrasts with the remaining 4 groups. The a-priori-defined contrasts will consist of the following 5 comparisons: A vs. E, A vs. B/C/D combined, A vs. B, A vs. C, and A vs. D. Thus, for each subsample, there will be 5 planned comparisons, and hence a total of 15 comparisons. We expect the largest differences in mean  $PTSD_{dx}$  scores between PTSD only (group A) and controls (Group E), but nonetheless, also expect the PTSD only group to have higher mean  $PTSD_{dx}$  scores than Groups B, C, and D.

In these analyses, models will be adjusted for potential confounding variables (e.g. current use of sleep medications) identified by use of student *t*-tests (or Wilcoxon tests) for continuous variables and chi-square tests for categorical variables. Given the 5 planned comparisons for each subsample, a modified p-value of 0.01 will be used to define statistical significance. While arbitrary, “validation” of the previously identified  $PTSD_{dx}$  neuromarker will be based on statistical significance as follows: (i) all 3 comparisons of Group A vs. Group B at  $p<0.01$ , AND at least 9 of the 12 remaining comparisons at  $p<0.01$ .

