In the second phase of this hypothesis, the approach used to identify the most promising  $PTSD_{dx}$  neuromarker described in Preliminary Studies will be applied to the much larger dataset of 656 veterans. For this analysis, Subsamples 1 and 2 will serve as training (development) samples, and Subsample 3 will serve as the validation sample. For subsample 1, ANCOVA will again be used to identify the 5 most promising  $PTSD_{dx}$  neuromarkers (based on corresponding *F* and *p*-values) rank ordered across the 5 planned comparisons described above. This process will be repeated for Subsample 2. From these results, the most promising  $PTSD_{dx}$  neuromarker will be selected based on the lowest aggregate rank scores across both subsamples and across all 5 planned comparisons. Once this  $PTSD_{dx}$  neuromarker is identified, it will be formally tested using the 5 defined planned comparisons within Subsample 3, and again using a *p*-value of  $<0.01$  to define statistical significance. In aggregate, these analyses will determine whether the originally identified  $PTSD_{dx}$  neuromarker can discriminate between veterans with and without PTSD, and whether a potentially

more promising  $PTSD_{dx}$  neuromarker is identified.

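### The Phase 1 validation rule for PTSD_dx counts p-values without a direction, so a large difference in the wrong or inconsistent direction would count as validation

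*Combined protocol and SAP*

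**What the plan says.** Section 3.5, Hypothesis 1.1, first phase, takes the PTSD_dx marker from the preliminary study and tests it in three random subsamples. The contrasts are "A vs. E, A vs. B/C/D combined, A vs. B, A vs. C, and A vs. D". Over the three subsamples "there will be 5 planned comparisons, and hence a total of 15 comparisons", and "a modified p-value of 0.01 will be used to define statistical significance".

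The direction is given as an expectation. The largest difference is foreseen against controls (E), and for Groups B, C and D the authors "also expect the PTSD only group to have higher mean" scores. For A vs. E only the size is stated; the direction is implied.

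The decision rule follows. Validation "will be based on statistical significance as follows: (i) all 3 comparisons of Group A vs. Group B", each below the 0.01 threshold. As a second condition, 9 or more of the other 12 contrasts must also fall below it. The expectation is not part of the rule.

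The second phase ranks new candidate markers in Subsamples 1 and 2 on F and p-values. The marker is "selected based on the lowest aggregate rank scores across both subsamples and across all 5 planned comparisons". It is then tested on the five contrasts in the held-out Subsample 3 at p<0.01. The plan requires no agreement of sign between contrasts, between training subsamples, or in Subsample 3.

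**The concern.** The first phase tests a fixed marker with a stated direction. If PTSD-only Veterans scored clearly lower than the other groups, that would be a failed replication, yet the written rule would score it as a success. The same holds for an inconsistent pattern, such as PTSD-only above controls but below the TBI and depression groups. No single cut-off on such a marker separates PTSD from non-PTSD, and Hypothesis 1.1 in section 1.0 is about sensitivity and specificity. This rule is the plan's only stated criterion for validating the original marker, so it should not rely on an analyst noticing a reversal.

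The second phase has a related gap. F carries no sign, so a marker could rank well while pointing in different directions in the two training subsamples. The selected marker is then carried into the dense-array study (Hypothesis 2 in section 3.5).

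**Working it through.** **Inputs from the plan.** Group sizes by subsample (table in section 3.5): A 36/36/35, B 42/42/42, C 29/29/29, D 26/27/27, E 86/85/85. Threshold p<0.01. Rule: 3 of 3 for A vs. B and at least 9 of the other 12.

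**The plan's own figures reproduce.** 0.05/5 = 0.01. 5 × 3 = 15 comparisons, and 15 − 3 = 12. The table columns sum to 219, 219 and 218. The plan gives no power calculation for the rule.

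**Assumptions.** Two-sided tests (sidedness is not stated; the plan uses ANCOVA and F), normal scores with a common SD, no covariates, and effect sizes of 0.3 to 1.2 SD.

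**One contrast by hand.** For A vs. B in Subsample 1, t = difference / √(1/36 + 1/42) = difference / 0.227 in SD units, on 219 − 5 = 214 df. The two-sided 0.01 critical value is 2.60, so the contrast counts when |difference| exceeds 2.60 × 0.227 = 0.59 SD. Only the absolute value enters. For a true difference of 0.8 SD in either direction the power is about 0.82, and all three A vs. B contrasts pass with probability about 0.82³ = 0.55. The 9-of-12 condition lowers this slightly.

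**Full rule, simulated (40,000 runs per scenario).**

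| PTSD-only vs. every other group | As written | With sign condition |
|---|---|---|
| No difference | 0% | 0% |
| 0.3 SD lower | 0.01% | 0% |
| 0.5 SD lower | 2% | 0% |
| 0.8 SD lower | 51% | 0% |
| 1.0 SD lower | 89% | 0% |
| 1.2 SD lower | 99% | 0% |
| 0.5/0.8/1.0/1.2 SD higher | 2/51/89/99% | 2/51/89/99% |

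The rule is symmetric in sign, and the sign condition costs nothing when PTSD-only is higher than every group.

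**Inconsistent pattern.** With A 1 SD below B, C and D but 1 SD above E, the rule passes in 89% as written and 0% with the condition.

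**Cost when Group C scores as high as or higher than A.** Let A exceed B, D and E by 1.2 SD. If C equals A, the pass rate goes from 86% to 85%. If C's shift is 20% larger than A's, it goes from 81% to 74%.

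**Which contrasts should carry a sign requirement in the second phase.** Take a genuine marker with A above B, D and E by 0.5 to 1.2 SD, and ask how often the sign is right in both training subsamples.

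| Group C | Required in all five contrasts | Required only vs. B, D, E |
|---|---|---|
| Equal to A | 25% | 92–100% |
| Shift 20% larger than A | 3–12% | 92–100% |

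Group C also has PTSD, so A vs. C is close to a coin-flip in each subsample when the two groups score alike.

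**The case against.** The direction is stated in the same section as the rule, a two-sided p-value with a stated direction is ordinary practice, and a reversal would show in the reported adjusted means. If one-sided tests were intended, the Phase 1 gap closes. This is fair as to intent, but the rule as written neither says so nor uses the expectation.

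A false pass also needs a large true reversal. At 0.3 to 0.5 SD the rule almost never passes in either direction, and nothing in the documents suggests that a large reversal exists. That stands, and it limits the point to a defect in the rule. It is not a prediction about the data.

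A reader might infer that the second phase also lets a reversed marker be validated. The documents do not support that. The ranking selects a marker and a held-out test in Subsample 3 follows. A new marker has no prior sign, so ranking on F is not wrong in itself. How often a sign-inconsistent marker would be selected depends on the number of candidates, which the plan does not give, so no percentage is offered here.

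A reader might also conclude that direction should be imposed on every contrast in both phases. For the second phase the 25% figure above argues against this.

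**Conclusion.** The point holds for the Phase 1 rule. It ignores sign, so a large real difference in the wrong or inconsistent direction would be declared validation: about 51% of the time at 0.8 SD lower and 89% at 1.0 SD lower, against 0% with a sign condition. These percentages rest on assumed effect sizes, two-sided tests and no covariates; the symmetry of the rule does not depend on the effect sizes. It would be wrong to infer that the rule is prone to chance validation, since a global null never passed. For the second phase, the missing sign requirement is a gap in marker selection, worth closing as a safeguard, and not an instance of false validation.

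**What to change.** **First phase.** State that a comparison counts toward validation only if p<0.01 and the PTSD-only adjusted mean is higher than the comparator's, and state this direction explicitly for A vs. E. The requirement includes A vs. C because the plan itself expects A to be higher there. The cost is one sentence and no new data. The only loss found is the modest one shown above when the PTSD-and-TBI group scores as high as or higher than PTSD-only (81% to 74% at 1.2 SD with C 20% higher).

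One gap remains. The rule tolerates three misses among the 12, so a marker higher in depression-only than in PTSD-only can still pass. With depression-only 1.2 SD above A, and A 1.2 SD above the rest, the pass rate falls from 98% to 19%, not to zero. The authors should decide whether that is acceptable.

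**Second phase.** Keep the ranking. Require the selected marker to have the same sign in A vs. B, A vs. D and A vs. E in both training subsamples, and require that sign in the Subsample 3 test. Do not impose it on A vs. C or on A vs. B/C/D combined, because Group C also has PTSD. This is one further sentence. Both changes should be made before the retrospective data are analysed.

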### **1.0 Objective and Specific Aims:**

This project evaluates novel PTSD biomarkers which are based on measures of coherent activity among the regions of cerebral cortex during sleep. In preliminary studies on EEG acquired during sleep from Veterans with PTSD alone as well as other co-morbidities, we have shown that the neuromarkers were highly sensitive/specific to the presence of PTSD, and highly sensitive to the severity of symptoms in PTSD group.

The overall goal of this project is to further validate these novel neurophysiology markers in retrospective and prospective studies. The Overall hypothesis to be studied is as follows:

**Specific Aim 1:** Formally establish the sensitivity/specificity of the novel PTSD neuromarkers by analyzing a large existing dataset

**Hypothesis 1.1:** Neuromarkers can distinguish PTSD from non-PTSD groups with clinically acceptable sensitivity and specificity.

**Hypothesis 1.2:** In PTSD group, Neuromarkers will strongly correlate with PTSD symptom severity and measures of functional outcome.

**Specific Aim 2:** Evaluate improvement on the performance of the neuromarkers using a dense array EEG montage [Prospective Study 1]

**Specific Aim 3:** Evaluate the sensitivity of Neuromarker to the improvements in PTSD symptoms

Hypothesis 2: Neuromarkers will strongly correlate with the improvement of PTSD symptoms

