## **2.2 Preliminary Studies**

In preliminary studies on EEG acquired during sleep from Veterans with PTSD alone (n=38), TBI alone (n=30), PTSD and TBI (n=25), and an aged matched no PTSD or TBI control group (n=38), we have shown that a set of neuromarkers were highly sensitive/specific to the presence of PTSD, and highly sensitive to the severity of symptoms in PTSD group.

The PTSD neuromarkers of this project are built from combination of regional brain coherence markers (BCM). BCM computation is based on the levels of coherence and synchronicity between pairs of scalp EEG activity. These coherence values were computed for the entire sleep study using

5-second sliding windows that were overlapped by 1 second. The frequency band spanned from 0.2 Hz to 50 Hz with a resolution of 0.2 Hz. Vectors of BCM were constructed over each of the five stages of sleep study (Awake [W], Rapid Eye Movement [REM], non-REM [NREM] stages N1, N2, and N3). Our analysis showed that the markers computed in awake and stage N2 sleep were significantly different in PTSD than the control group and also produced the highest level of correlation with the PTSD symptom.

The following figure shows the excellent capability of the PTSD diagnostic Neuromarker ( $PTSD_{dx}$ ) and PTSD severity marker ( $PTSD_{sev}$ ) in differentiating Controls from PTSD, and in correlation with symptoms, respectively.

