## **4.0 Human Subjects**

### **4.1 General Characteristics**

The project has three groups of human subjects’ involvement:

1. A retrospective study, where the analyses will be applied to a large existing database of health-related and functional outcome measures, as well as sleep EEG recordings. Database contains sleep EEG recordings from Veterans with PTSD only (n=107), with TBI only (n=126), with both PTSD and TBI (n=87), with depression only (n=80), and controls (no PTSD/TBI/Depression; n=256. The inclusion of records from TBI and depression only groups is to provide training data for the biomarker to become maximally sensitive and specific to PTSD in the presence of co-morbidities such as depression and TBI.
2. Prospective study 1 with up to 25 PTSD and control PTSD (n=10) and control (n=10) where we will evaluate potential improvement on the performance of the biomarkers using a dense array (up to 64 channel) EEG montage. For each participant, we will perform 2 sets of sleep studies that will be at least one week apart.
3. Prospective study 2 in a cohort (n=60) of Veterans undergoing psychotherapy, where we will evaluate the sensitivity of biomarkers to the improvements in PTSD symptoms, and other functional and HRQoL measures, in response to psychotherapy. These participants will undergo sleep studies at four times of time (a) Within one week before initiation of their treatment protocol; (b) Within one week after their first therapy session; (c) at the conclusion of their treatment phase; and (d) About three months after their last therapy sessions

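### The Phase 1 validation rule for Hypothesis 1.1 makes only PTSD versus TBI mandatory, so either the control contrast or the depression contrast (not both) can fail in all three subsamples and the marker still counts as validated

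*Combined protocol and SAP*

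**What the plan says.** The Hypothesis 1.1 heading in section 3.5 states that the marker "will discriminate PTSD patients from control subjects without PTSD". Section 1.0 words the same hypothesis more broadly: "Neuromarkers can distinguish PTSD from non-PTSD groups with clinically acceptable sensitivity and specificity".

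Phase 1 takes the marker "previously identified in our preliminary study of 76 veterans, and evaluate it separately in all 3 subsamples". Each third has five planned ANCOVA contrasts: A vs. E, A vs. B/C/D combined, A vs. B, A vs. C and A vs. D. That makes 15 tests, each at p<0.01. On the expected ordering the plan says "We expect the largest differences in mean" scores between A and E, and it also expects A to score above B, C and D.

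Validation, by a rule that the plan itself calls arbitrary, needs "all 3 comparisons of Group A vs. Group B" and "at least 9 of the 12 remaining comparisons", all at p<0.01. No other contrast is named as required. The text has an item (i) but no item (ii).

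Section 4.1 explains that the TBI and depression records are there to make the marker "maximally sensitive and specific to PTSD in the presence of co-morbidities such as depression and TBI".

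Phase 2 selects a new marker in Subsamples 1 and 2 and tests it in Subsample 3. It names no mandatory contrast either.

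**The concern.** The hypothesis is about PTSD against controls, but the one mandatory contrast is PTSD against TBI. Depression stands beside TBI as a specificity target in section 4.1, yet the rule does not protect it. The second-phase text says that the two phases together will show whether the original marker separates veterans with and without PTSD. A marker could be declared validated with no significant result on the contrast that the heading names, or with none against depression.

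A second, lesser matter is that the Phase 1 marker is fixed beforehand, so Phase 1 trains nothing and has no need of the split. Requiring significance in each third makes a negative verdict hard to interpret, because it may reflect only the size of the subsamples.

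**Working it through.** **The plan's own figures.** The level 0.01 equals 0.05/5, taking a family level of 0.05, which the plan does not state. The counts are 5 × 3 = 15 tests, and 15 − 3 = 12 after the mandatory A-B tests. The subsample table adds up to 219, 219 and 218, total 656.

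**Counting; no assumption needed.** The 12 tests are 3 each of A-E, A-C, A-D and A-B/C/D. Nine are enough, so three may fail, which is exactly one whole contrast.
- Of the 2^12 = 4096 significance patterns, 299 have at least 9 successes.
- One of these has no significant A-E test, and one has no significant A-D test.
- None has both, because 12 − 6 = 6 < 9.

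**How likely each gap is.** The documents give no effect size in the available text, so the differences below are assumptions in SD units. The simulation uses the planned subsample sizes (A 36/36/35, B 42/42/42, C 29/29/29, D 26/27/27, E 86/85/85), common variance, no covariates, two-sided 0.01 and significance in the expected direction, with at least 200,000 runs per scenario. Ranges reflect B/C/D averaged equally or weighted by n.

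| Scenario | Rule met |
|---|---|
| All contrasts 0.5 | 1.5% |
| All contrasts 0.8 | 50-51% |
| All contrasts 1.0 | 89% |
| C equals A, others 0.8 | 12-15% |
| C equals A, others 1.0 | 45-53% |
| A equals D; A-E, A-B, A-C all 1.0 | 46-59% |
| Same, all 0.8 | 13-19% |
| A equals D; A-E, A-B 1.0; C 0.5 below A | about 2% |
| A equals D and C; A-E, A-B 1.0 | about 0% |
| A equals E; B, C, D all 1.0 lower | 57-58% |

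In the 46-59% row, 97-98% of the passes had none of the three A-D tests significant. If Group E is made the mandatory group in place of B, that row is unchanged at 46-59%. In the equal-contrast rows, no run passed without a significant A-E test.

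**Full sample (107/126/87/80/256).** Requiring A-E, A-B and A-D each at p<0.01 once gives power of 73% with all contrasts at 0.5 and 99.8% at 0.8. A marker with A equal to D, or A equal to E, passes in 0.5% of runs.

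**The bar this sets.** The smallest significant observed difference is t(0.995, N−5) × sqrt(1/nA + 1/nX).
- A-E, full sample: 2.58 × sqrt(1/107 + 1/256) = 2.58 × 0.115 = 0.30.
- A-E, one third: 2.60 × sqrt(1/36 + 1/86) = 2.60 × 0.199 = 0.52.
- Under equal-variance normality, d = 0.30 gives AUC = Φ(0.30/√2) = 0.58, or sensitivity = specificity = Φ(0.15) = 56%.

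**The case against.** The strongest reply has four parts.

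1. **The A-E gap hardly ever opens.** A pass with no significant A-E test needs all nine A-C, A-D and A-B/C/D tests significant, while the plan expects A-E to be the largest difference. The 57-58% scenario contradicts that expectation. This stands: for A-E the fault is one of logic. Group B may also be a slip for Group E, as the heading and the unpaired item (i) could suggest. The documents do not settle that, and the A-D gap survives either reading.

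2. **The A-D gap is conditional.** It needs depression-only veterans to score like PTSD-only veterans while those with PTSD and TBI score well below PTSD only. If all three A-C tests fail, the allowance is used up and every A-D test must be significant. This also stands, although the plan itself predicts A above C.

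3. **The strict rule is partly a design preference.** Disjoint thirds tested with a frozen marker are a form of internal replication, though from one source, and the true effect may be large. At an assumed 1.2 with equal contrasts the planned rule passes about 99% of the time. A reader might infer that Phase 1 is underpowered; the documents do not support that, because the effect size is not in the available text.

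4. **Overlap with the preliminary sample is not shown.** A reader might infer that the 76 preliminary veterans, which matches 38 PTSD plus 38 controls in section 2.2, are among the 656. The text does not say so. Section 3.4 says the preliminary studies used the PCL-M, while section 3.3 lists the PCL-5 for the repository, which is weak evidence against overlap. It is a question to check, not a fault.

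**Conclusion.** The mismatch between rule and hypothesis is certain, because it rests on counting alone. Validation guarantees neither separation from controls nor separation from depression. It would be wrong to read this as both contrasts failing together: two wholly failed contrasts leave at most 6 of 12.

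The practical exposure is to depression. It is material (46-59%) only under an assumed 1.0 SD for A-E, A-B and A-C with A equal to D, and it nearly disappears as Group C approaches A. The power figures are likewise illustrations at assumed effects.

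Phase 1 does not determine whether Phase 2 or the prospective studies proceed, and Hypothesis 2 carries forward the Phase 2 marker. What is at stake is the Phase 1 conclusion. The rule should be corrected, but it does not undermine the rest of the project.

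**What to change.** **Main change.** Confirm whether Group B in the rule was meant to be Group E. In either case make A vs. E mandatory, with A vs. B and A vs. D as required specificity contrasts. This is SAP wording only.

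**Secondary.** Keep the split for Phase 2. For Phase 1 also report every contrast, including A-C and A-B/C/D, in the full sample with effect size and 95% CI, and AUC for A-E, beside the three subsample results.

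**Where to apply the threshold.** The sponsor should decide this openly. Requiring A-D in all three thirds caps the pass rate at about 36% for a true difference of 0.8 and 75% for 1.0. Requiring the three contrasts once in the full sample raises power to the figures shown above. The cost is a lower bar (observed A-E d of about 0.30, AUC about 0.58), and three-fold replication becomes descriptive. Significance must then not be presented as the clinically acceptable accuracy that section 1.0 asks for.

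**Separate check.** Establish from the coded records whether any of the 76 preliminary veterans are among the 656, and exclude them from Phase 1 if so. At most this removes 38 of 107 in Group A and 38 of 256 in Group E. No new data are needed.
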